4.5 Intervention

Melatonin

To our knowledge, there are no studies reporting on the use of exogenous melatonin in adult survivors of childhood cancer. Studies have reported low nocturnal salivary⁷⁴ and 24-hour plasma⁷⁵ levels of endogenous melatonin in childhood survivors of craniopharyngioma. Increased daytime sleepiness was associated with decreased nocturnal melatonin levels in these survivors and supplementation with 6mg of exogenous melatonin resulted in improved daytime sleepiness.⁷⁴

Data are lacking on the pharmacokinetics and pharmacodynamics of melatonin in cancer survivors, although among adults individual variation is apparent. The ability to synthesize melatonin varies among individuals with low secretors (18 to 40pg/mL) and high secretors (54 to 75pg/mL) distinguished.⁷⁶ Immediate release exogenous melatonin has rapid absorption, with peak levels occurring 20-30 minutes after administration,

though estimates of its half-life in serum range from 30 to 60 minutes.⁷⁶ Approximately 90% of the supplement is cleared by hepatic first-pass metabolism and involves oxidation by CYP1A2 and CYP2C19.⁷⁷ When formulated with absorption retarding binders, melatonin availability mimics that of normal nocturnal secretion.^{78,79} Sustained release melatonin circumvents the fast clearance of the hormone and essentially mimics physiological patterns of endogenous secretion of the hormone. Sustained release products have been demonstrated to maintain, high, near physiological, plasmas levels for 5 to 7 hours.⁸⁰

The optimal dosing of melatonin is unclear. Clinically, melatonin has two primary uses including soporific (3mg) which is sleep inducing and phase shifting which may be achieved with a lower dose (0.5mg)⁸¹ That is, lower doses are commonly used for shift phasing purposes while higher doses are found most effective in promoting sleep onset. The most common dose used in studies for free running sleep disorder was 3 mg and the duration of treatment ranged from 1 month to 6 years.⁸² Pharmacological doses of melatonin range from 0.1-10mg and doses greater than 0.5mg produce endogenous levels greater than those observed physiologically. At the high end of the dosage range melatonin levels can be thousands of times higher than normal. 3mg of melatonin may produce peak levels that are 10 times physiological concentrations.⁸³ Attenburrow et al⁸⁴ demonstrated that 1mg but not 0.3mg improved sleep in middle-aged adults, suggesting a supraphysiological threshold is necessary for sleep-promoting effects.

The active melatonin product will be purchased in its marketed form from Natrol®, a reputable manufacturer in the United States. For the current study Natrol® 3mg time release melatonin will be utilized. Additional ingredients included in the Natrol® 3 mg time release melatonin tablets includes Vitamin B6 (from pyridoxine hydrochloride), cellulose, dibasic calcium phosphate, hypromellose, silica, stearic acid, magnesium stearate, methylcellulose and glycerin. Melatonin is considered a nutraceutical and is not FDA approved for prevention, diagnosis or treatment of disease.

UPM Pharmaceuticals, Inc. will develop and manufacture placebo tablets matching the melatonin product to achieve similar shape, weight and color of the Natrol® brand melatonin tablet. UPM Pharmaceuticals will test the potency, content uniformity, and timed release dissolution of the melatonin in its marketed form. Both active melatonin and placebo will be shipped to St. Jude Pharmaceutical Services, and these bulk shipments will be repackaged into appropriate containers for dispensing to patients, with appropriate labeling. All study drugs will be stored and processed by Pharmaceutical Services at SJCRH. Both melatonin and placebo will be labeled in a manner that will assure blinding of the study. Melatonin/placebo will be dispensed in 1 bottle, containing 60 tablets. Medication will be sent via FedEx (2 day delivery) or other commercial courier at 2-month intervals. [name] (co-Investigator) has extensive

experience with randomized clinical drug trials and will manage the processing and blinded distribution of melatonin/placebo to participants.

Participants will be instructed to take one 3mg tablet of time release melatonin or placebo each night during the 6-month trial. Consistent with procedures described by Wade et al⁵⁵ participants will be instructed to take one tablet of melatonin/placebo orally, 1-2 hours before initiating sleep onset, preferably at the same time each night.

4.5.1 Adherence

Medication Event Monitoring Systems

Electronic monitors are often considered the “gold standard”, with respect to adherence measurement.⁸⁵ Medication event monitoring systems (MEMS), a type of electronic monitor, registers the date and time when a medication vial cap is opened,⁸⁶ thus, providing real-time monitoring and documentation of medication adherence. Despite this, MEMS caps are a proxy for adherence measurement, as there is no confirmation that a participant actually takes the medication after opening the pill bottle. Therefore, it is recommended that electronic monitoring be used in conjunction with other adherence measures.

Pill Count

Pills counts have been widely used to assess adherence to medication regimens. Pill counts compare the amount of medication remaining in a container with the amount that would be left if all prescribed medication was consumed. A study staff member will contact each participant by telephone or electronic mail. He or she will be asked to self-report the number of melatonin/placebo pills remaining in their medication container. The self-reported pill counts will be obtained approximately every 30 days while on the study. Adherence for study drug will be documented through the use of a telephone log.

Problem Solving

Participants who do not demonstrate at least 80% adherence to the prescribed intervention, as measured by monthly pill counts, will be contacted via telephone to participate in a problem-solving exercise. [name] will monitor participant adherence throughout the interventions trial and will contact participants who demonstrate poor adherence behaviors to problem-solve potential barriers to adherence, as well as identify and discuss possible solutions (see problem solving phone script).

4.5.2 Side Effect Monitoring

Side Effect Profile

Reports of adverse events will be monitored. The research participant will be contacted at the end of the first week on study drug then biweekly for the duration of the study. Adverse event information will be collected throughout the study by participant reporting and direct questioning using the patient report of incidence of side effects (PRISE), frequency and intensity of side effect rating (FISER), and global rating of side effects burden (GRSEB). The PRISE form assesses the presence of side effects for a variety of biological systems. For each of the nine organ/function systems (gastrointestinal, nervous system, heart, eyes/ears, skin, genital/urinary, sleep, sexual functioning, and other), the participant indicates the presence of a side effect, and if present, the tolerability of the side effect (tolerable or distressing). The FISER and GRSEB assess three domains of medication side effect impact: frequency, intensity, and burden. Each domain is rated on a 7-point Likert scale (i.e. Frequency, ranging from no side effects to present all the time; Intensity, ranging from no side effects to intolerable; and Burden, ranging from no impairment to unable to function due to side effects). Reliability and validity have been reported.

4.6 Dose Modifications

There will be no dose modifications for melatonin or placebo. Treatment will be discontinued if a participant reports an adverse event that is not tolerable which the investigator deems related to the study drug. The participant will end treatment on the study and arrangements will be made for the return of unused melatonin/placebo.

4.7 Concomitant Therapy

Females may take oral contraceptives. If at any time during the six months of study treatment with melatonin/placebo, the participant must start the use of any of the medications listed in the exclusion criteria for medical conditions not present at the time of enrollment, he/she will be taken off-treatment. These medications include: 1) benzodiazepines or other CNS depressants; 2) fluvoxamine; 3) anticoagulants 4) immuno-suppressants or corticosteroids and 5) Nifedipine (Procardia XL)

5.0 DRUG INFORMATION

Melatonin

Source and Pharmacology: Melatonin (N-Acetyl-5-Methoxytryptamine) is a neurohormone produced in the pineal gland that is involved in the promotion of sleep. It is naturally released during the dark hours of the normal day-night cycle. It is also thought to play a role in regulating the secretion of growth hormones and gonadotropic hormones. Melatonin may also possess some antioxidant properties. Melatonin undergoes significant first-pass metabolism (up to 60%) with an oral dosage form, and is metabolized into two inactive metabolites: 6-hydroxymelatonin and N-acetyl serotonin. Clearance is severely reduced in patients with hepatic insufficiency. Melatonin is mostly excreted in the urine as the inactive metabolite 6-hydroxymelatonin. Adults experience approximately a 37% decline in melatonin production between the ages of 20 and 70 years.

In vitro data suggests that melatonin may inhibit the CYP1A2 isoenzyme and may affect the disposition of CYP2C9. Use with caution in individuals taking medications influenced by these enzyme systems. Melatonin may interact with calcium channel blockers leading to an increase in blood pressure. Possible immune-stimulating effects of melatonin may interfere with immunosuppressant therapy.

Formulation and Stability: Melatonin 3 mg time release tablets will be used. The tablets are to be stored at controlled room temperature and are stable according to manufacturer's labeling.

Supplier: Commercially available from various manufacturers. For the current study Natrol® 3mg time release melatonin will be utilized. Additional ingredients included in the Natrol® 3 mg time release melatonin tablets includes Vitamin B6 (from pyridoxine hydrochloride), cellulose, dibasic calcium phosphate, hypromellose, silica, stearic acid, magnesium stearate, methylcellulose and glycerin. Melatonin is considered a nutraceutical and is not FDA approved for prevention, diagnosis or treatment of disease.

Toxicity: Drug toxicities with melatonin are rare. Serious side effects have not been reported but long term studies have not been performed. The most common side effects of using melatonin are drowsiness and confusion, especially if used with other CNS sedating drugs. Other toxicities that have been associated with melatonin are headache, hypersensitivity, tachycardia, hypothermia, and increased seizure activity. Melatonin may reduce glucose tolerance and insulin sensitivity. Use with caution in individuals with a history of bleeding disorders, hemostatic disorders and in individuals taking anticoagulant medications (warfarin, aspirin, NSAIDs or antiplatelet agents) or antidiabetic agents or insulin. Avoid use in women who are pregnant or may become pregnant.

Dosage and Route of Administration: Participants will be instructed to take one 3mg time released tablet of melatonin or placebo by mouth approximately 1-2 hours before initiating sleep onset, preferably at the same time each night.

Placebo

Placebo tablets to match the melatonin will be comprised of inert substances. Placebo will be developed and manufactured by UPM Pharmaceuticals, Inc. [name], Director of Quality Assurance at the St. Jude GMP Facility, has reviewed the proposed placebo development methods to assure that Good Manufacturing Processes are used.

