3.2 Exclusion Criteria

- 3.2.1 Participant has a known allergy to melatonin or any ingredients of the study product or placebo
- 3.2.2 Participant currently is taking Melatonin
- 3.2.2 Participant has known sleep apnea or medically treated sleep disorder (e.g. restless leg syndrome)

- 3.2.3 Participant has known diabetes mellitus – insulin treated
- 3.2.3 Participant has uncontrolled seizure disorder in past 12 months
- 3.2.4 Participant has current reported illicit drug or alcohol abuse or dependence
- 3.2.5 Participant has current major psychiatric illness (i.e. schizophrenia, bipolar disorder)
- 3.2.6 Participant is currently receiving treatment with benzodiazepines or other CNS depressants
- 3.2.7 Participant is currently receiving treatment with fluvoxamine
- 3.2.8 Participant is currently receiving treatment with anticoagulants (e.g. Coumadin)
- 3.2.9 Participant is currently receiving treatment with immunosuppressants or corticosteroids
- 3.2.10 Participant is currently receiving treatment with Nifedipine (Procardia XL®)
- 3.2.11 Participant is employed in a position that requires night work (i.e. 10pm to 6am)
- 3.2.12 Female participants who are pregnant or lactating/nursing
- 3.2.13 Participant has a history of neurologic event (i.e. traumatic brain injury) unrelated to cancer or its treatment
- 3.2.14 Participant has a sensory impairment (vision, hearing) that prohibits completion of neurocognitive examination

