3.5 Enrollment on Study

A member of the study team will confirm potential participant eligibility as defined in Section 3.1-3.2, complete and sign the 'Participant Eligibility Checklist'. The study team will enter the Eligibility Checklist information into the Patient Protocol Manager (PPM) system. Initial eligibility will be reviewed, and a research participant-specific consent form will be generated. The complete signed Eligibility Checklist and consent/assent form(s) must be faxed or sent electronically to the CPDMO to complete the enrollment process.

The CPDMO is staffed 7:30 am-5:00 pm CST, Monday through Friday. A staff member is available at [REDACTED] for enrollment during the weekend.

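### Known hepatic insufficiency is not an exclusion, although the protocol says it severely reduces melatonin clearance and the dose cannot be changed: a cheap, minor safety addition

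*Combined protocol and SAP*

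**What the plan says.** Section 5.0 (Drug Information) says of melatonin: "Clearance is severely reduced in patients with hepatic insufficiency". It also says: "Melatonin undergoes significant first-pass metabolism (up to 60%) with an oral dosage form". Section 4.5 gives a second, larger first-pass figure of roughly 90%, in text on immediate-release melatonin, and names the hepatic enzymes CYP1A2 and CYP2C19.

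Eligibility rests on two lists. The Protocol Summary has 13 exclusions, and section 3.2 runs from 3.2.1 to 3.2.14. Neither has an item on liver disease, hepatic insufficiency or liver function, and nor do sections 3.1, 4.7 or 8.1. Section 3.5 ties the entry decision to these lists: "A member of the study team will confirm potential participant eligibility as defined in Section 3.1-3.2".

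The dose is 3 mg nightly for six months. Section 4.6 states: "There will be no dose modifications for melatonin or placebo". The response it provides is to stop treatment for an intolerable adverse event judged related to study drug.

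**The concern.** The drug section names a condition that raises exposure, the entry criteria do not screen for it, and the dose cannot be lowered once a person is in. A survivor with a recorded diagnosis can be randomised to six months of nightly dosing at raised exposure without departing from any written criterion.

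The issue is participant safety and, secondarily, test performance. Section 5.0 says: "The most common side effects of using melatonin are drowsiness and confusion". Section 6.3 schedules the 6-month neurocognitive testing while participants are still taking study drug.

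The omission also sits oddly with another criterion. Fluvoxamine is excluded at entry (3.2.7) and, if started later, takes the participant off treatment (4.7). The plan gives no reason. However, the paper that section 4.5 cites for the hepatic enzymes (reference 77) says in its title that fluvoxamine raises serum melatonin. The natural inference is that raised exposure through impaired hepatic metabolism was thought worth excluding when a drug causes it.

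**Working it through.** The plan states no figure on this point, so there is none to reproduce. The check compares the text and then bounds the size and the cost.

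**1. Which section 5.0 statements reach the exclusion lists?**

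- Full or partial match: sedating drugs ("Participant is currently receiving treatment with benzodiazepines or other CNS depressants"), seizures, allergy, insulin, anticoagulants, immunosuppressants, one calcium channel blocker (nifedipine), pregnancy.
- No match: hepatic insufficiency; bleeding disorders; aspirin, NSAIDs and antiplatelet agents; non-insulin antidiabetic agents; other medicines affected by the CYP enzymes.

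The hepatic statement is one of several without an exclusion.

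**2. Exposure.** Let L be the first-pass loss and s the share of it removed by liver disease. The documents do not give s, so it is assumed here at a quarter, a half and all. The available fraction goes from 1 − L to 1 − L(1 − s), so 3 mg acts like 3 × [1 − L(1 − s)] / (1 − L).

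| s | L = 0.60 (section 5.0) | L = 0.90 (section 4.5) |
|---|---|---|
| 1/4 | 3 × 0.55/0.40 = 4.1 mg | 3 × 0.325/0.10 = 9.8 mg |
| 1/2 | 3 × 0.70/0.40 = 5.3 mg | 3 × 0.55/0.10 = 16.5 mg |
| all | 3 × 1/0.40 = 7.5 mg | 3 × 1/0.10 = 30 mg |

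These figures come before any slower systemic clearance, for which the documents give no multiple. Section 4.5 says: "Pharmacological doses of melatonin range from 0.1-10mg". On the 60% figure every row lies inside that range. On the 90% figure two of the three do not.

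**3. People.** No prevalence is given. Per 1% of prevalence:

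- If 395 are randomised 1:1 (section 11.0: 131 + 131 + 133): 395/2 × 0.01 = 2.0 people on melatonin.
- If the 25% attrition is applied to the evaluable targets (assumed): 131/0.75 = 175, 131/0.75 = 175 and 133/0.75 = 178, total 528; 528/2 × 0.01 = 2.6.
- If all 987 enrolled were randomised: 987/2 × 0.01 = 4.9, an outer bound.

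These are people exposed, not people harmed.

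**4. Primary comparison.** If 1% of one arm lost a full SD (assumed), that arm's mean would move 0.01 × 1 = 0.01 SD, against the 0.66 SD target.

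**5. Cost of the exclusion in power.** With n per arm, power = Φ[(δ/σ)√(n/2) − z]. Prevalence is assumed at up to 10%.

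- Primary test, Cohort 1 or 2 (δ = 0.66, σ = 1, two-sided α = 0.05/6, z = 2.638). At 131 evaluable: 0.66 × √32.75 − 2.638 = 1.139, power 87.3%. At 117.9 (10% excluded and not replaced): 0.66 × √29.475 − 2.638 = 0.945, power 82.8%.
- Sleep onset latency, Cohort 3 (15 minutes, SD 27.7, α = 0.05): 87.7% at 133 evaluable, 84.2% with 10% excluded and not replaced.

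Both stay above the planned 80%. The plan's own inputs give more than 80% at 131, which is a separate matter and on the safe side. If excluded people are replaced, the 987 rises to 987/0.99 = 997 at 1% prevalence and 987/0.90 = 1,097 at 10%.

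**The case against.** The case for leaving the text alone has four parts.

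**The investigator can already act.** Section 8.1.5 allows removal when continuing would be harmful or the study is not in the participant's best interest, and neither ground is limited to problems arising on study. History and physical precede randomisation, full records are available (6.1), and section 3.6 already takes some people off study between baseline and randomisation. This stands: the plan has the means. What it lacks is a requirement. A reader might infer that nothing could stop a known case from being dosed; the documents do not support that.

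**The hepatic sentence is descriptive.** It sits under pharmacology and carries no caution, while an explicit caution such as "Use with caution in individuals with a history of bleeding disorders, hemostatic disorders" has no exclusion either. This stands too. A reader might infer that every other section 5.0 warning became an exclusion and only this one was missed; the comparison above shows otherwise. The argument for the change is the stated severity and the fluvoxamine parallel, not a broken pattern.

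**Melatonin is well tolerated.** Section 2.2.3 reports 10 mg for 28 days with no side-effect difference from placebo, and meta-analyses with no significant difference in common events. Section 5.0 calls toxicities rare, and its statement on drowsiness and confusion adds that they arise especially with other sedating drugs, which are excluded. This limits the likely harm. It does not settle the matter: the 10 mg trial was short and in healthy adults, and section 5.0 says long-term studies have not been done.

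**The forms are not in the documents.** The pre-screening form and eligibility checklist may already ask about liver disease. That cannot be ruled out, so the fix is worded conditionally.

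**Conclusion.** The gap is real and minor. As written, a survivor with known hepatic insufficiency is eligible, and keeping that person out depends on unguided discretion. Excluding the disease cause of raised exposure is consistent with excluding fluvoxamine, though the reason for the fluvoxamine criterion is inferred.

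Two stronger readings should be resisted. One is that affected participants would be harmed: no harm is shown, reported toxicity is low, and the number is unknown and probably small. The other, in the opposite direction, is that exposure would stay safely below 10 mg. That holds only on the 60% figure, and the 90% figure comes from text on immediate-release melatonin while the trial uses a time-release product. The documents therefore do not establish exposure within the cited range, nor do they establish that it goes beyond it.

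The effect on the primary comparison is negligible. The size rests on assumed values for prevalence, the share of first-pass loss removed, the number randomised and the 1 SD loss.

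**What to change.** - Add to section 3.2, as 3.2.15, and to the Protocol Summary exclusions, as item 14: *Participant has known hepatic insufficiency (a diagnosis in the medical record or made at the SJLIFE history and physical).*
- Add the matching question to the mailed pre-screening form and the Participant Eligibility Checklist, if it is not already there. The answer comes from information available before randomisation, so no new test is needed.

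The cost is two criterion lines, one form question, one checklist item and routine IRB review of the revision. A few candidates become ineligible. Any recorded diagnosis excludes regardless of grade, which spares staff from grading but is broader than the pharmacology may require. Undiagnosed cases are not caught. A sentence in section 4.7 for onset during treatment is optional, since 8.1.5 and 8.1.7 partly cover it.

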3.1 Inclusion Criteria

3.1.1 A St Jude Life participant who was previously treated at SJCRH.

3.1.2 Participant is 10 or more years from diagnosis.

3.1.3. Participant is ≥ 18 years of age.

3.1.4 Participant is able to speak and understand the English language.

3.1.5 Participant has a FSIQ score >79 .

3.1.6 Cohort 1 participant:

- a. Has neurocognitive impairment defined as performance on at least one measure of attention, memory, and/or executive functioning \leq 10th percentile.
- b. Is absent of delayed sleep onset latency defined as an inability to fall asleep within 30 minutes $<$ once a week during the past month.

Cohort 2 participant:

- a. Has neurocognitive impairment defined as performance on at least one measure of attention, memory, and/ or executive functioning \leq 10th percentile.
- b. Has delayed sleep onset latency defined as self-report of an inability to fall asleep within 30 minutes \geq once a week during the past month.

Cohort 3 participant:

- a. Is absent of neurocognitive impairment defined as performance $>$ 10th percentile on all six measures of attention, memory, and executive functioning.
- b. Has delayed sleep onset latency defined as self-report of an inability to fall asleep within 30 minutes \geq once a week during the past month.

3.1.7 Female participant of childbearing age must not be pregnant (confirmed by serum or urine pregnancy test within 1 week of eligibility) or lactating.

3.1.8 Female research participant of childbearing age and male research participant of child fathering potential must agree to use safe contraceptive methods.

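### Pregnancy status is verified only at entry: nothing scheduled during about 26 weeks of home dosing asks about it, and no off-treatment rule names it

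*Combined protocol and SAP*

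**What the plan says.** The drug information in section 5.0 (Toxicity) carries the warning "Avoid use in women who are pregnant or may become pregnant".

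**Controls at entry**
- Inclusion criterion 3.1.7 requires that a woman of childbearing age is not pregnant, "confirmed by serum or urine pregnancy test within 1 week of eligibility".
- Criterion 3.1.8 requires that women of childbearing age and men who could father a child "must agree to use safe contraceptive methods".
- Criterion 3.2.12 excludes "Female participants who are pregnant or lactating/nursing".
- Table D places the pregnancy test in the baseline column. Its note presents the test as an institutional condition of eligibility.

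**During dosing**
- On supply, section 4.5 says tablets are "dispensed in 1 bottle, containing 60 tablets", and that "Medication will be sent via FedEx (2 day delivery) or other commercial courier at 2-month intervals".
- Section 6.2 plans a side-effect contact after the first week and then every two weeks. The symptom form used (4.5.2) covers "gastrointestinal, nervous system, heart, eyes/ears, skin, genital/urinary, sleep, sexual functioning, and other".
- Table E has no pregnancy row, and Appendix I marks the pregnancy test at baseline only.

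**Stopping and reporting**
- Section 4.6: "Treatment will be discontinued if a participant reports an adverse event that is not tolerable which the investigator deems related to the study drug".
- Section 4.7 takes a participant off treatment if one of the listed excluded medications has to be started.
- Section 8.1 does not list pregnancy but includes investigator discretion (8.1.5).
- Section 9 does not name pregnancy. Section 9.1 counts a congenital anomaly as a serious event.

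**The concern.** The warning in 5.0 covers women who may become pregnant as well as those who already are, so it applies throughout treatment. The plan's verification stops once the participant is randomized. A woman who conceives on study and does not raise it herself could keep taking tablets, and be sent another bottle, because nobody is scheduled to ask.

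The plan already recognizes that an entry exclusion can arise during dosing. For anticoagulants, section 5.0 advises only caution, yet starting one is a named reason to come off treatment in 4.7. Pregnancy is also an entry exclusion and carries the stronger instruction to avoid use, but it has no matching rule.

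What is at stake is participant safety and consistent handling by staff. The efficacy comparison is not in question.

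**Working it through.** The plan gives no figure to reproduce here. The check sets the sections side by side and works out the schedule.

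**1. Length of dosing without verification.** Six months is 365.25 / 2 / 7 = 26.1 weeks. Section 6.3 allows an extension of at most two weeks, so the maximum is about 28 weeks.

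**2. Resupply.** 26 × 7 = 182 nights, and 182 / 60 = 3.03, so about three bottles (180 tablets), sent at about months 0, 2 and 4. The second and third go out after the entry test, with no pregnancy check stated before release.

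**3. Contacts already planned.** One call after week 1 and then every two weeks gives weeks 1, 3, …, 25, which is 13 calls. None of the nine systems on the symptom form is pregnancy, although the genital/urinary and other items would let a participant mention it. The pill-count contacts (4.5.1) ask how many tablets remain. The 6-month provider visit includes an interim history (6.3) whose content is not specified.

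**4. Interval between questions if the existing calls are used.** The nominal interval is 2 weeks. With each call allowed ±7 days, the longest gap between two consecutive calls is 2 + 1 + 1 = 4 weeks.

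**5. Stopping rules compared**

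| Event during dosing | Named off-treatment rule |
|---|---|
| Intolerable, drug-related adverse event | Yes (4.6) |
| Newly started excluded medication | Yes (4.7) |
| Pregnancy | None; investigator discretion (8.1.5) is available |

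**6. Number of cases (illustration on assumed inputs).** The documents give neither the share of participants who could conceive nor a pregnancy rate. Assume 25% to 50% could conceive and that 1% to 6% of them per year become pregnant despite contraception, over half a year:
- Low: 395 × 0.25 × 0.01 × 0.5 = 0.5
- High: 395 × 0.50 × 0.06 × 0.5 = 5.9
- On melatonin, at 1:1 allocation: about 0.2 to 3.0

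The 395 is the evaluable number, and more may be dosed. As a ceiling, if all 987 targeted enrollees were dosed, the same inputs give 987 × 0.25 × 0.01 × 0.5 = 1.2 to 987 × 0.50 × 0.06 × 0.5 = 14.8. In either case this is 0.25 × 0.01 × 0.5 = 0.1% to 0.50 × 0.06 × 0.5 = 1.5% of those dosed.

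**The case against.** The best defence has four parts.

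**Contraception is the main control, and it runs through dosing.** This stands. A reader might infer that the plan does nothing about pregnancy after entry. Criterion 3.1.8 does not support that, and 4.7 expressly allows oral contraceptives during treatment. What is confined to entry is verification: no later check of pregnancy status or contraceptive use is scheduled.

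**A known pregnancy can already be acted on.** This also stands. Two of the examples in 8.1.5, harm from continuing and the participant's best interest, fit a pregnancy once the 5.0 warning is considered. A reader might go further and infer that using 8.1.5 would force the participant off study and lose her 6-month data. That reading is not secure. The heading of section 8.0 covers removal from therapy as well as off-study criteria, and one 8.1.5 example, a needed but disallowed medication, is the event that 4.7 handles as off treatment. The remaining weakness is that discretion works only once someone knows.

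**Reporting may be covered.** A reader might infer that pregnancies and their outcomes go entirely unreported. The documents do not show that. A congenital anomaly is a serious event under 9.1, and the sentence in 9.2 on recording serious events has no end date; the six-month limit applies to trial-related adverse events. Section 9.1 also refers to unanticipated events involving risk to others. The consent pages, the parent SJLIFE protocol and the separate monitoring plan were not available and may tell participants to report a pregnancy and stop. This reduces the reporting part to a clarification. It does not answer the scheduling part, because call content and off-treatment rules belong in the protocol.

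**The risk is small.** The documents describe a marketed supplement with rare toxicity and give no evidence of fetal harm, and few cases are likely. That limits the weight of the point. It is no argument against a change that costs one question per call.

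**Conclusion.** The point holds as an inexpensive safety improvement. In the visible protocol, pregnancy status is verified once, at entry. No test, question or resupply check is then scheduled over about 26 weeks of home dosing, and no named off-treatment rule applies if a pregnancy occurs.

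The 26 weeks is the length of planned dosing. A reader might take it as expected exposure in pregnancy, but many women would know and say so sooner. Nor is it a documented interval between pregnancy enquiries, because nothing says that the 6-month history asks.

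Few cases are expected relative to the number treated. The illustrative counts rest wholly on assumed inputs and cannot be derived from the documents. Confidence is moderate, because unseen consent or parent-protocol text could already cover part of this.

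**What to change.** 1. Add a pregnancy question for women who could conceive to the existing side-effect calls (week 1, then every two weeks), and state it in 6.2, Table E and Appendix I.
2. Add pregnancy to 4.7 as a reason to stop tablets, which also stops further shipments, and say that the 6-month assessment is kept.
3. As a secondary clarification, add a line to section 9 on reporting an on-study pregnancy and its outcome. If the consent form already covers this, align the two.

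The cost is one short amendment, one extra question per call and, if the section 9 line is adopted, some follow-up of rare cases beyond six months. Randomization, endpoints, sample size and analysis do not change.
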